##### *Integrated analysis*

For the integrated analysis, these rules will be applied:

For subjects randomized to Nusinersen in Part 1 then Part 1 and Part 2 will be considered as a one period and any data available will be used for any imputation. However, for subjects who were randomized to receive Sham in Part 1 then the two periods (Part 1 and 2) will be considered separately and no imputation will be allowed i.e., no interpolation between the 2 periods.

The imputation of missing data will follow these rules:

- 1) If a subject has any milestones missing at baseline then the missing milestone will be imputed using the median baseline value within the age of SMA onset ( $\leq 6$  months,  $>6$  months). for the correspondent milestone level
- 2) If a subject has any missing milestones at any other visit that is not last visit then the missing milestone will be imputed using a linear interpolation at the milestone level for any actual scheduled study visits (for last visit, please see bullet point 4).
- 3) Perform windowing selecting the closest non-missing milestone to the target date
- 4) If a subject has a least one milestone observed but some milestones are missing, then any missing milestones at the last visit will be imputed using the lowest observed value for that milestone, assigned within the age of SMA onset ( $\leq 6$  months,  $>6$  months) to which the subject belongs, at that windowed analysis visit. If only a date is available and all of the milestones are missing, then no imputation will be performed.

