After informed consent is obtained, subjects will undergo a screening evaluation no greater than 28 days prior to administration of the first dose of study treatment. Subjects who meet the eligibility criteria will be randomized to receive Nusinersen or sham procedure. Subjects will be admitted to the study site on Part 1 Day 1, undergo predose evaluations, and then receive an LP injection of study treatment or sham procedure. Subjects will return to the study site on Days 15, 29, 64, 183, and 302 for follow-up evaluations and subsequent injections or sham procedures. For subjects receiving Nusinersen or sham procedure, a CSF sample will be taken predose on each injection day in a manner that maintains the blind.

After the study treatment dosing or sham procedure on Day 1, subjects will remain at the study site for at least 24 hours for safety monitoring. Following all subsequent injections, all subjects will remain at the study site for at least 6 hours postdose for safety monitoring.

Safety monitoring will occur on the day following each injection of study treatment or sham procedure. Subjects receiving the dosing or sham procedure on Days 15, 29, 64, 183, and 302 will be monitored by telephone contact on Days 16, 30, 65, 184, and 303.

In addition, subjects will also be monitored through telephone contact throughout the duration of the study.

An End of Part 1 Evaluation will occur up to 4 months after the last dose of Nusinersen or sham procedure, or sooner (if the Sponsor decides to terminate Part 1 early based on emergent data from the Nusinersen clinical development program, as described below). Subjects who terminate early from Part 1 of the study will be encouraged to complete the End of Part 1 Evaluation assessments at the time of withdrawal.

After completing End of Part 1 Evaluation assessments according to the study schedule or sooner, if emergent data from the Nusinersen clinical

CONFIDENTIAL

The information contained herein may not be used, disclosed, or published without the written consent of Biogen MA Inc.

development program necessitate the early termination of Part 1 by the Sponsor, all eligible subjects may elect to enroll in Part 2. All subjects enrolled in the study at the time that the Sponsor terminates Part 1 will be considered Part 1 completers. The next study evaluation for those subjects will serve as an End of Part 1 Evaluation, which may occur at any time prior to the next scheduled Part 1 study evaluation.

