eligible for Study ISIS 396443-CS4. The maintenance dose interval (once every 4 months) was selected based on the estimated spinal tissue and CSF drug half-life (4 to 6 months) and was selected to maintain spinal cord tissue levels of Nusinersen at a steady-state level within the estimated pharmacologically active range. In Part 1, maintenance doses will be given on Day 183 and Day 302, for a total of 6 doses over approximately 10 months. Subjects who were receiving Nusinersen in Part 1 will continue receiving maintenance doses in Part 2 every 4 months. Subjects who were receiving sham in Part 1 will receive maintenance doses starting on Day 183 of Part 2.

Table 1 Nusinersen Dose Volume To Be Injected

Age	Estimated CSF Volume (mL)	Injection Volume (mL)	Dose (mg)
0-3 months (0-90 days)	120	4	9.6
3-6 months (91-182 days)	130	4.3	10.3
6-12 months (183-365 days)	135	4.5	10.8
12-24 months (366-730 days)	140	4.7	11.3
>24 months (>730 days)	150	5.0	12.0

Source: [[Matsuzawa 2001](#)]

CSF = cerebrospinal fluid.

Study Location: Global, multicenter

Number of Planned Subjects: In Part 1, up to 21 subjects are planned (14 Nusinersen; 7 sham procedure).

In Part 2, up to 21 subjects are planned (21 Nusinersen).

Study Population: Part 1 of this study will be conducted in subjects who have clinical signs and symptoms of SMA at ≤ 6 months of age or at > 6 months of age and who are not eligible for the clinical studies ISIS 396443-CS3B or ISIS 396443-CS4.

Part 2 will include only subjects who participated in Part 1 and completed their End of Part 1 Evaluation assessments. Subjects enrolling in Part 2 must meet the Part 2-specific criteria.

Detailed eligibility criteria are described in Section 8.

CONFIDENTIAL

The information contained herein may not be used, disclosed, or published without the written consent of Biogen MA Inc.

Treatment Groups:	
In Part 1, subjects will receive either Nusinersen intrathecally or sham-procedure control in a 2:1 ratio. Randomization will be balanced for the stratification factor (age of symptom onset >6 months versus ≤6 months). A single dose level of 12 mg Nusinersen will be scaled by age at the time of dosing for each subject.
 
In Part 2, all subjects will receive open-label Nusinersen. A single dose level of 12 mg Nusinersen will be scaled by age at the time of dosing for each subject.

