#### *Integrated analysis*

The HINE motor milestones, growth parameters and CGI, laboratory data, CSF and Plasma concentrations integrated analyses will be windowed as follows:

Study days  $\leq 1$  will be labelled Baseline

- Study days  $> 1$  to  $\leq 22$  will be labelled Day 15
- Study days  $> 22$  to  $\leq 47$  will be labelled Day 29
- Study days  $> 47$  to  $\leq 123$  will be labelled Day 64
- Study days  $> 123$  to  $\leq 242$  will be labelled Day 183
- Study days  $> 242$  to  $\leq 362$  will be labelled Day 302
- Study days  $> 362$  to  $\leq 482$  will be labelled Day 422
- Study days  $> 482$  to  $\leq 600$  will be labelled Day 540
- Study days  $> 600$  to  $\leq 719$  will be labelled Day 659
- Study days  $> 719$  to  $\leq 838$  will be labelled Day 778
- Study days  $> 838$  to  $\leq 958$  will be labelled Day 898
- Study days  $> 958$  to  $\leq 1078$  will be labelled Day 1018
- Study days  $> 1078$  to  $\leq 1198$  will be labelled Day 1138

If multiple results are allocated into the same window then the closest non-missing result to the target date will be chosen.

In order to account for the denominator across the analysis visits, an Efficacy set for each windowed analysis visit (Day X) will be defined as: a subset of subjects in the Safety set who have the opportunity to be assessed at the Day X visit, where the lower bound for the windowed analysis visit are denoted: L= lower. Specifically, it will include all subjects with a time difference of at

least L days between the date of first dose and the end of Part 2. A subject who has died or withdrawn will be included provided that there is a difference of at least L days between the date of first dose and the end of Part 2. In a situation where the subject was known to have withdrawn from the study at a date within the window due to rolling over to commercial drug then they will be excluded from the corresponding Efficacy set and subsequent analysis visit Efficacy sets.

An evaluable set will be defined for each analysis visit as the subset of subjects in the Efficacy set at the analysis visit who meet the following criteria:

- Value assigned from the windowing
- Subject who died or discontinued from the study – no imputation of efficacy data will be performed for such subjects and they will be considered non-responders.

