#### 4.5.1 HINE motor milestones

HINE Section 2 comprises eight tests for motor milestones: head control, sitting, voluntary grasp, ability to kick in supine position, rolling, crawling, standing, and walking.

There are 26 possible motor milestones that can be achieved using this schema (presented below). A subject whose results all appear in the first column (unable to maintain head upright, cannot sit, no grasp, etc.) has not achieved any motor milestone. A subject whose results all appear in the second column (head wobbles, sits with support at hips, uses the whole hand for a voluntary grasp, etc.) has achieved 8 motor milestones. A subject whose results all appear in the third column (head maintained upright all the time, props when sitting, index finger and thumb but immature grasp, etc.) has achieved 16 motor milestones.

*Attainment of motor milestones assessed by Section 2 of the Hammersmith Infant Neurological Examination (HINE)*

For the integrated analysis, the HINE motor milestones analyses will be presented by windowed analysis visits (see section 4.1).

The definition of a motor milestone responder is based upon the motor milestones categories in Section 2 of the HINE, with the exclusion of voluntary grasp as follows:

- Subject demonstrates at least a 2-point increase in the category of ability to kick or increase to the maximal score on that category (touching toes), or a 1-point increase in the motor milestones category of head control, rolling, sitting, crawling, standing, or walking AND
- Among the motor milestone categories, with the exclusion of voluntary grasp, there are more categories where there is improvement, as defined in (i) below, than there are categories where there is worsening (as defined below).
- Subjects who die or withdraw from the study on or prior to the visit will be counted as non-responders and will be included in the denominator

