## **8 Sample size justification**

There are no formal sample size calculations for this study. Sample size is based upon feasibility.

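### SAP 4.5.1 interpolates missing HINE items before windowing, so an imputed fraction can displace a score observed in the same window and change responder status at that visit

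*SAP*

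**What the plan says.** The rules form a numbered list in SAP 4.5.1 (Missing data, Integrated analysis). Rule 1 fills missing baseline items. Rule 2 covers any later visit except the last: "the missing milestone will be imputed using a linear interpolation at the milestone level for any actual scheduled study visits". Rule 3 follows: "Perform windowing selecting the closest non-missing milestone to the target date". Rule 4 then fills items missing at the last visit with the lowest observed score at that windowed visit. Nothing brings an interpolated item back to a whole score, and nothing ranks observed scores above imputed ones.

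SAP 4.1 (Integrated analysis) sets the windows. Day 183 takes study days above 123 and up to 242. The section expects more than one result per window: "If multiple results are allocated into the same window then the closest non-missing result to the target date will be chosen". It also has its own rule for an empty window: if windowing assigns nothing and the child has a later assessment, the value at the preceding analysis visit is carried forward.

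The responder definition in 4.5.1 leaves out voluntary grasp. It accepts "a 1-point increase in the motor milestones category of head control, rolling, sitting, crawling, standing, or walking", with a separate test for kicking, provided that more categories improve than worsen. Outside kicking, worsening means a fall of one point or more.

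On timing, the Protocol Synopsis (Study Design) says of the End of Part 1 evaluation after early termination: "which may occur at any time prior to the next scheduled Part 1 study evaluation". SAP section 2 reports that sham children left Part 1 first, whatever their dosing day, while Nusinersen children moved over on their own dose schedule. SAP sections 1 and 1.3 say that Part 2 also ends early.

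**The concern.** Rule 3 chooses among non-missing values, but by then rule 2 has already made the missing item non-missing and placed it on or near the target day. An observed score elsewhere in the window then loses to a number that nobody recorded. HINE items take whole scores only, while the interpolated number is usually a fraction, and both the response and the worsening tests need a full point.

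At stake are the windowed by-visit responder proportions, the by-visit tables of individual milestones, the total score by visit, and the visit of first response. In columns this small, one reclassified child is visible.

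**Working it through.** **Inputs.** Windows come from SAP 4.1, the thresholds and rule order from SAP 4.5.1, and the HINE visit days from the schedules of activities. Planned group sizes come from the Protocol Synopsis: "In Part 1, up to 21 subjects are planned (14 Nusinersen; 7 sham procedure". The visit days and scores in the examples are assumptions chosen to show the mechanism.

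**Check on the responder rule.** I counted improved and worsened categories separately, leaving out grasp. This reading gives the stated answer for all eight of the closing worked examples in 4.5.1.

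**Formula.** With score v0 on day t0 and v1 on day t1, the interpolated score on day t is v0 + (v1 - v0) x (t - t0)/(t1 - t0).

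**Hidden gain.** Take one category other than kicking or grasp. The score is 0 at baseline and Day 64, the item is missing at Day 183, and a 1 is observed at an End of Part 1 visit on day t1. The fraction is (183 - 64)/(t1 - 64):
- t1 = 200: 119/136 = 0.875
- t1 = 230: 119/166 = 0.717
- t1 = 242: 119/178 = 0.669

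All three days lie in the Day 183 window. The interpolated value is on the target day, so rule 3 takes it. The change is below 1, so this category gives no response, although the only observed score in the window is a one-point gain. For every t1 from 184 to 242 (59 days) the fraction is below 1, so the result is the same. If no other category qualifies, the child is a non-responder at Day 183.

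**Limit of the effect.** A two-point gain survives: 2 x 0.669 = 1.338, which is still at least 1. The problem is confined to one-point differences in these six categories.

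**Opposite direction.** Rolling is observed one point up at Day 183. Head control is 2 at baseline and Day 64, missing at Day 183, and observed as 1 on day 235. The interpolated head control is 2 - 119/171 = 1.304, a fall of 0.696, which is not worsening. The SAP order gives one improved and no worsened category, so the child is a responder. With observed scores there is one of each, so the child is a non-responder.

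**Part 2 route.** A previous-Nusinersen child scores 1 on study day 421, has the item missing on day 540, and scores 2 at an early-termination visit on day 570. Days 540 and 570 share the Day 540 window (above 482, up to 600). The interpolated score is 1 + 119/149 = 1.799, a gain below 1, and it displaces the observed 2.

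**Size.** One child in a seven-child column is 1/7, or about 14 percentage points.

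**The case against.** The strongest reply is that non-missing in rule 3 may mean observed. The problem would then vanish. The SAP does not say so: rule 4 in the same list uses the word observed and rule 3 does not, and the numbering puts interpolation first. Equally, a reader might infer that rule 3 was evidently written to find the nearest real observation. The text does not show that intent either. Estimating status at Day 183 rather than borrowing a score from up to 59 days later is a position one could defend. It sits badly with 4.1, however, which assigns values to windows and imputes only when none is assigned.

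The reach is also limited, and several wider readings fail:
- A reader might infer that an early End of Part 1 visit exposes both arms, and might attach a frequency by assuming that the visit falls evenly between scheduled visits. SAP section 2 moved Nusinersen children on their dose schedule, and Protocol 9.3 aims to keep their four-month interval. Four months after Day 64, 183 or 302 is close to the next target day, so the visit falls in the next window. This route is mainly a sham-group matter.
- A reader might infer that the baseline-to-last shift table and the last-available-assessment responder analysis are affected. They use the last assessment, which rule 2 excludes.
- A reader might treat the by-visit responder table as the leading efficacy display. The SAP ranks no exploratory endpoint and says "There are no formal sample size calculations for this study".

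One ambiguity stands. The bar on imputation for previous-sham children reads most naturally as covering only interpolation across Parts 1 and 2. On a stricter reading, rule 2 does not apply to them at all, and only the Part 2 route for previous-Nusinersen children remains.

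**Conclusion.** The point holds for the rules as written. The stated order lets an interpolated fraction displace an observed score, and that can misclassify a child at one window in either direction. It takes three things together: an item missing at a non-last visit, a second HINE in the same window with that item observed farther from the target day, and that item being decisive for the child's status. On the regular schedule each window holds one HINE visit, so this arises mainly at early End of Part 1 visits for previous-sham children and at Part 2 early-termination visits for either group. When it happens, one child moves a seven-child column by about 14 points. The documents give no basis for saying how often. A gain hidden at one window reappears later if it persists and is observed.

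The conclusion assumes that non-missing includes imputed values, and that interpolation within a part is allowed for previous-sham children. It is a worthwhile correction to exploratory displays and does not touch the primary safety objective.

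**What to change.** In SAP 4.5.1 (Integrated analysis), assign observed item scores to windows first, and state that an observed score always takes precedence. Impute only for a window with no observed score for that item. For those windows keep a single rule, reconciled with 4.1, which already carries forward the preceding analysis visit. Carry-forward keeps items on whole HINE scores, so no separate rounding rule is needed. The same edit should say plainly whether imputation within a part is allowed for previous-sham children.

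The cost is a short text change and a reordering of the programming; no new data are needed. There are two downsides. A window may use an observed score farther from its target day, and carry-forward shows no change in a window that truly had no assessment, so a gain there appears one window late.

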#### 4.5.2 WHO motor milestones

The WHO motor milestones are a set of six milestones in motor development, all of which would be expected to be attained by age 18 months in healthy children. The individual milestones are:

- Sitting without support
- Standing with assistance
- Hands and knees crawling
- Walking with assistance
- Standing alone
- Walking alone

The motor milestones are assessed at visits, after the V4 protocol approval at sites, using the WHO motor milestone criteria [WHO Multicentre Growth Reference Study Group 2006]. As part of the assessment, the examiner records an overall rating of the subject's emotional state and then for each milestone one of the following four classifications:

- No (inability) – Child tried but failed to perform the milestone
- No (refusal) – Child refused to perform despite being calm and alert
- Yes – Child was able to perform the milestone

- Unable to test – Could not be tested because of irritability, drowsiness or sickness.

In an effort try and attach greater precision to the dates of first achievement of milestones, the caregivers are recording the first date they observe the child achieving each milestone and this is additionally captured in the CRF

#### *Missing values*

No imputation will be performed for missing data.

### **4.6 Clinical Global Impression of Change (Investigator and Caregiver assessments)**

The Clinical Global Impression of Change (CGIC) is assessed at specific visit. At each visit the investigator and the subject's caregiver each score how the subject has changed compared to 'admission to the project'. The assessment is scored on a 7- point ordinal scale (1= Very much improved, 2 = "Much improved", 3 = "Minimally improved", 4= "No change from baseline", 5= "Minimally worse", 6= "Much worse", 7 = "Very much worse").

In order to investigate response on these scales, three definitions of responder will be defined: "Much improved": Responder ( $\leq 2$ ) versus Non-responder ( $\geq 3$ ), "Any improvement": Responder ( $\leq 3$ ) versus Non-responder ( $\geq 4$ ), "No worsening": Responder ( $\leq 4$ ) versus Non-responder ( $\geq 5$ ). At the start of Part 2 for subjects that were previously on sham, the question was changed to be how the subject has changed compared to 'admission to Part 2, while for subjects remaining on Nusinersen, the question remained how the subject has changed compared to 'admission to the Part 1.'

The proportion of subjects who were responders based on the "Much improved", 'Any improvement' and 'No worsening' definition of responder will be presented by windowed analysis visit.

These analyses will be performed separately for investigators and caregivers' responses. The analyses will also be stratified based on age of SMA onset ( $\leq 6$  months,  $>6$  months). In Part 2 the data will be collected referring to the admission to Part 1 or 2 respectively depending on the original treatment in Part 1: previous Sham subjects will be scored in comparison to 'admission to Part 2', previous Nusinersen subjects will be scored in comparison to 'admission to Part 1

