Summary statistics will be presented throughout. For continuous endpoints, summary statistics will generally include number of subjects with data, mean, standard deviation, median, minimum and maximum. The mean changes from baseline will be estimated with 95% confidence intervals. For categorical endpoints, summary statistics will generally include: number of subjects dosed, number of subjects with data, and the percentage of those with data in each category. Frequency distributions will be presented as appropriate.

The statistical software, SAS® version 9.4 or above, will be used for all summaries and statistical analyses.

For Part 2, a limited number of summaries will be produced. The approach will be to preserve the Part 1 study groupings as follows for Safety and Efficacy population:

- Previous control.
- Previous ISIS 396443.
- Total (previous control and previous ISIS 396443).

For the integrated analyses, the Safety displays will be grouped as follows:

- Previous control, Part 1, from their first sham procedure in Part 1.
- Previous control, Part 2, from their first ISIS 396443 dose in Part 2.
- Previous ISIS 396443, Part 1 and 2, from their first ISIS 396443 dose in Part 1.
- Total (Previous control Part 2 and previous ISIS 396443 Part 1 and 2)

For the integrated analyses, the Efficacy displays will be grouped as follows:

- Previous control, Part 1, from their first sham procedure in Part 1.
- Previous control, Part 2, from their first ISIS 396443 dose in Part 2.
- Previous control, Part 1 and 2, from their first sham procedure in Part 1.
- Previous ISIS 396443, Part 1 and 2, from their first ISIS 396443 dose in Part 1.

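### In the integrated CGIC tables, the previous-control column spanning both parts joins ratings made against Part 1 entry with ratings made against Part 2 entry

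*SAP*

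**What the plan says.** SAP 4.6 opens with one reference point for everyone: "At each visit the investigator and the subject's caregiver each score how the subject has changed compared to" the child's entry into the study. It then records that the wording altered once children moved into the open-label part. For one group, "for subjects that were previously on sham, the question was changed to be how the subject has changed compared to" their Part 2 entry. For the other group, "for subjects remaining on Nusinersen, the question remained how the subject has changed compared to" their Part 1 entry. The closing lines of 4.6 repeat the split: "previous Sham subjects will be scored in comparison to" Part 2 entry, and nusinersen children in comparison to Part 1 entry.

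The response categories do not change ("The assessment is scored on a 7- point ordinal scale"). Three responder cut-offs are applied: scores of 2 or lower, 3 or lower, and 4 or lower (the last is 'No worsening'). For each, the proportion under that "definition of responder will be presented by windowed analysis visit", separately for investigator and caregiver and also by age of onset.

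SAP 4.1 lists CGI among the data that go through the integrated windows. SAP 2 gives four columns for integrated efficacy displays: previous control in Part 1; previous control in Part 2; "Previous control, Part 1 and 2, from their first sham procedure in Part 1"; and previous nusinersen across both parts. Section 4.6 contains no exception, footnote or conversion rule for the third of these.

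**The concern.** For HINE or growth, a column running from the first sham is workable, because change can be recalculated from the stored Part 1 baseline. A CGIC score is itself a judgement against a named starting point. Programming cannot convert a rating of change since Part 2 entry into change since Part 1 entry.

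The effect on interpretation has a direction. Suppose a control child declines on sham and is then stable on nusinersen. Rated against Part 2 entry, the score is 4 (no change), which is a 'No worsening' response. Rated against Part 1 entry, the same child would be worse and a non-responder. Such a course is plausible: Protocol 5.4 describes an overall decline with age in SMA outcome measures. The next column, previous nusinersen across both parts, keeps the Part 1 reference throughout, so a reader comparing early with delayed start would see loss during the sham period removed from one side only.

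**Working it through.** The plan states no figure on this point, so there is nothing to reproduce. The check is where the ratings fall.

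**Inputs**
- Part 1 CGIC days: 64, 183, 302 and End of Part 1 (SAP 1.4, Part 1 schedule).
- Part 2 CGIC days for previous controls: 64, 183, 302, 421, 540, 659, 778 and final follow-up at 897 (SAP 1.4, Part 2 schedule for the sham group).
- Windows from SAP 4.1: Day 64 is >47 to ≤123; Day 183 is >123 to ≤242; Day 302 is >242 to ≤362; Day 422 is >362 to ≤482; Day 540 is >482 to ≤600; and so on. The result closest to the target day is kept.
- Switch day T, counted from first sham. The documents do not give it. SAP 2 says sham children left Part 1 without regard to planned dosing days, so it varies. **Assumption:** T from 100 to 422, with End of Part 1 and Part 2 Day 1 both on study day T.

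**Formula:** Part 2 Day d falls on study day T + d − 1.

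| T | Part 1 ratings (study day → window) | First three Part 2 ratings (study day → window) |
|---|---|---|
| 100 | 64→64, 100→64 | 163→183, 282→302, 401→422 |
| 150 | 64→64, 150→183 | 213→183, 332→302, 451→422 |
| 200 | 64→64, 183→183, 200→183 | 263→302, 382→422, 501→540 |
| 250 | 64→64, 183→183, 250→302 | 313→302, 432→422, 551→540 |
| 300 | 64→64, 183→183, 300→302 | 363→422, 482→422, 601→659 |
| 350 | 64→64, 183→183, 302→302, 350→302 | 413→422, 532→540, 651→659 |
| 422 | 64→64, 183→183, 302→302, 422→422 | 485→540, 604→659, 723→778 |

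**Mixing between children, after keeping the closest rating**
- Day 64: Part 1 reference only. A Part 2 rating would need T + 63 ≤ 123, that is T ≤ 60.
- Day 183: T = 100 contributes a Part 2 rating (day 163); T = 200 contributes a Part 1 rating (day 183).
- Day 302: T = 100 contributes a Part 2 rating (day 282); T = 350 a Part 1 rating (day 302).
- Day 422: T = 350 contributes a Part 2 rating (day 413); T = 422 a Part 1 rating. A Part 1 rating here needs T > 362.
- Day 540 onward: Part 2 reference only.

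**Sensitivity of a single cell.** In the Day 183 window, T = 150 offers day 150 (183 − 150 = 33 days off) and day 213 (213 − 183 = 30 days off), so the Part 2 rating is kept. T = 155 offers day 155 (28 days off) and day 218 (35 days off), so the Part 1 rating is kept. A five-day shift in T changes the reference point.

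**Size in a rate.** With the 7 controls planned, one child is 1/7 = 14 percentage points. As an illustration with assumed counts, if 4 of 7 respond against Part 2 entry but only 2 of 7 would against Part 1 entry, the reported rate is 57% instead of 29%.

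**The case against.** The best defence is that the change of reference point is deliberate, disclosed and coherent. Each child is rated against entry to the part in which nusinersen was first received. The pooled safety analysis in Protocol 16 uses the same logic, with the Part 1 baseline for active children and the Part 2 baseline for sham children. The column label may also be only a generic statement of which period's data enter, not a claim about what the raters compared with. Three of the four integrated columns each have one consistent reference point, CGIC is exploratory, and no CGIC test is specified.

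Most of this stands. It shows that the collection rule is sensible and that the harm is limited. It does not rescue the one column that joins both periods: whatever its label is taken to mean, its cells hold ratings with different starting points, and the plan says neither to separate nor to mark them.

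Two stronger readings are tempting, and the documents do not support either.
- *The Part 2 Total also mixes reference points.* SAP 2 lists "Total (previous control and previous ISIS 396443") for Part 2 displays, and 7/21 = 33% of planned children are controls. But the integrated efficacy grouping has no Total, only a limited number of Part 2 summaries is promised, and 4.6 names no Part 2-only CGIC table, whereas 4.5.1 does name Part 2-only displays for HINE. The two groups' scheduled Part 2 CGIC days also never coincide: the smallest gap is 120 − 64 = 56 days, and 56 − 14 = 42 days remain with both visits at their 7-day limits. Pooling would need windowed Part 2 days, relabelled end-of-study visits or a last-visit summary. The 33% describes no table that the SAP specifies.
- *The groups are scored on different scales.* There is one 7-point scale with one set of cut-offs; only the reference point differs.

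**Conclusion.** The point holds for one column: the integrated CGIC display of previous controls across both parts. As planned, its responder rates refer to change since Part 1 entry in the early windows, possibly to a mixture in the Day 183 to Day 422 windows, and to change since Part 2 entry after that. The direction of the resulting bias depends on what happened on sham. For a child who declined there, it favours the combined control column.

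Which windows are affected rests on the assumed switch days; that the reference point changes does not. The 14-point step uses the planned 7 controls, and the 57% against 29% contrast is illustrative only. Severity is minor: the endpoint is exploratory, the summaries are descriptive, no error rate is involved, and the change of question is disclosed in 4.6 although not carried into the column structure.

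**What to change.** In SAP 4.6, for both investigator and caregiver CGIC and in the age-of-onset strata:
1. Omit the integrated column that joins Parts 1 and 2 for previous controls.
2. Keep the other three columns and state the reference point in each header: Part 1 entry for previous control in Part 1, Part 2 entry for previous control in Part 2, and Part 1 entry for previous nusinersen across both parts.
3. Limit the opening sentence on admission to the project to Part 1 ratings and to nusinersen children.
4. Add that any Part 2-only CGIC table will show no Total, or that its Total will be labelled as change since entry to the part in which nusinersen was first received.

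The cost is a few lines of SAP text and one column fewer per table. No data are lost, because every rating in the omitted column still appears in one of the two separate previous-control columns, subject to the windowing there.
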